- **Aim 1: To determine the impact of 60Hz subthalamic deep brain stimulation on gait kinematics using wearable sensors**
 - Aim 1.1: To determine whether 60Hz STN-DBS elicits a differential response in gait kinematics compared to high frequency
 - Aim 1.2: To determine the influence of 60Hz STN-DBS and levodopa on gait kinematics
- **Aim 2: To develop machine learning models to predict optimal subthalamic deep brain stimulation frequency based on wearable sensor profiles of baseline Parkinson's motor symptoms**
 - Aim 2.1: To develop machine learning models to predict gait response to 60Hz stimulation without additional testing
 - Aim 2.2: To develop machine learning models to predict best stimulation frequency (60Hz vs. high frequency).

This study will set the stage for developing a randomized trial that would assess a new paradigm for selecting DBS patients for 60Hz stimulation prior to surgery, conducting initial programming and other elaborate programming approaches under this stimulation mode, and achieving programming optimization using sensors, through a data-driven approach. In addition, the results may indicate that certain PD phenotypic subtypes are most suitable for 60Hz DBS.

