2.3.3 ASSESSMENT OF POTENTIAL RISKS AND BENEFITS

Potential Benefits:

Expected Outcomes: Aim 1. We would have extensively investigated the impact of 60Hz stimulation on several gait spatiotemporal domains (e.g., pace, turning, postural sway) and relate it to other stimulation features (e.g., activated electrode contacts, therapeutic amplitudes) using wearable sensors. We will also determine the influence that levodopa has on 60Hz stimulation in the context of kinematic gait changes. These results can help facilitate the application of this stimulation to certain PD-DBS subpopulations. Aim 2. Our results will allow for instantaneous recommendations by artificial intelligence on which stimulation frequency is best suitable for a subject based on *a priori* sensor measurements of motor symptoms. The ranking provided can guide clinical evaluations and potentially reduce the amount of time needed for programming by changing the “trial and error” paradigm to a sensor guided paradigm with either 60Hz or HFS initiated from the outset.

Potential Risks:

Subjects will be closely monitored following administration of carbidopa/levodopa 25/100mg tablet(s) to ensure any side effects are minimized and addressed immediately.

Any stimulation side effect will immediately be alleviated with reduction in DBS amplitude. All assessments will be done at amplitudes below the side effect threshold. Furthermore, all sensor assessments will be conducted in a control setting with the research coordinator and Principal investigator present at all times to minimize risk any risk of falling during the gait assessment.

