9 STATISTICAL CONSIDERATIONS

9.1 STATISTICAL HYPOTHESES

Aim 1. Our preliminary study established that gait and rest tremor are important factors to determine whether patients benefit from 60Hz stimulation or high frequency stimulation (38). However, the degree to which stimulation parameters affect gait parameters is not well established. In Aim 1, we will test the *hypothesis* that certain gait parameters are differentially affected between 60Hz and high frequency STN-DBS at various electrode contact configurations. In addition, in our preliminary analysis, we observed a modest reduction in dopaminergic medications in patients on 60Hz stimulation (12). Hence, we will also test the *hypothesis* that for some patients, the addition of levodopa in combination with 60Hz stimulation produces a synergistic improvement in certain gait domains.

Aim 2. Our preliminary data suggested that there is a link between the patient's baseline motor symptomatology measured by the MDS-UPDRS III ratings and the best stimulation frequency (60 Hz or HFS) chosen for the patient based on intensive clinical evaluations, which remained unchanged for an average of 12 months. In Aim 2, we test the *hypothesis* that a subject's gait kinematics on 60Hz stimulation can be predicted with statistically significant accuracy using gait measurements on high frequency stimulation. In addition, we will test the *hypothesis* that the best stimulation frequency (60Hz or HFS stimulation), which yields improvement among various gait parameters, can be predicted using objective sensor data collected at baseline. We define baseline motor performance as the severity of motor symptoms in the levodopa OFF and ON state without stimulation. In the remainder of this proposal, for simplicity we refer to 60 Hz stimulation and high frequency stimulation (130-180Hz) as low frequency (LFS) and high frequency (HFS), respectively.

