Aim 2.1. We will utilize the raw data collected during Phase II to develop regression models, under both ON and OFF medication states for all contact pairs. The top panel in Figure 2 presents the overview of Aim 2.1; the goal of this sub-Aim is to predict the gait parameters for patients on low frequency by using the gait sensor measurements obtained on high frequency. Additional independent variables/regressors include general patient/disease characteristics such as age, gender, and disease duration. We will also build models under both ON and OFF medications. To develop the regression models, we use non-linear regression analysis based on random forest (RF) classifier. RF is based on an ensemble of decision trees, referred to as a 'forest,' where predictions for any new observation are obtained from averaging the predictions of individual trees (56). Generally, RF models are not prone to overfitting and are robust against noisy or high-dimensional datasets (57). In addition, they are generally interpretable, allowing for further examination of results and easier subject subtyping with respect to symptomology. However, to assure that the RF based models are the best performing models, we also develop models based on some of the other machine learning techniques, such as neural networks (56), and use them as benchmarks. If needed, to improve model performance we will perform model building in RF models to identify and include the most important parameters (38). We will use techniques such as cross-validation (e.g., leave-one-out) and bootstrapping to examine the generalizability of the models and acquire confidence intervals for the predicted values. Lastly, we will compare the best performing models obtained for both ON and OFF medications and their most important contributing parameters to further investigate the interaction of medications and stimulation frequency.

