Aim 2.2. Similar to Aim 2.1, in this sub-Aim we conduct regression analysis to predict gait parameters. However, in this sub-Aim, gait parameters are predicted on low and high frequency in the context of ON and OFF medication conditions using baseline bradykinesia, tremor, and gait sensor measurements, plus MDS-UPDRS III rigidity and axial sub scores. Patient and disease characteristics will be used as regressors. Again, models will be based on RF classifier, where other modeling techniques, such as neural networks, will be used as benchmarks. The best performing parameters identified in Aim 2.1 will be used to guide the model building in this sub-Aim. Also, aforementioned performance enhancing techniques will be used, if possible, and confidence intervals will be generated using bootstrapping. These models will be able to predict the best stimulation frequency and contact pairs for the patient immediately after baseline evaluations and provide a confidence level. Similar to Aim 2.1, we will

develop these models with and without accounting for PD medications to further quantify their impact and provide additional options for patients.

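### Aim 2.2 has no minimum difference, no no-preference outcome and no test against one frequency for all, so good gait predictions would not show that the best frequency is predictable

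*Combined protocol and SAP*

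**What the plan says.** Predicting the best frequency is one of the primary endpoints in the Synopsis (Section 1.1). Section 2.1 words the sub-aim as a choice between two options: "To develop machine learning models to predict best stimulation frequency (60Hz vs. high frequency"). Section 9.1 makes it a hypothesis to be tested: "the best stimulation frequency (60Hz or HFS stimulation), which yields improvement among various gait parameters, can be predicted using objective sensor data collected at baseline".

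The analysis in Section 9.4.2 is a regression, not a classification: "gait parameters are predicted on low and high frequency in the context of ON and OFF medication conditions". The regressors are baseline sensor measurements, MDS-UPDRS III sub-scores and patient characteristics. On uncertainty it says "confidence intervals will be generated using bootstrapping". It then says of the output: "These models will be able to predict the best stimulation frequency and contact pairs for the patient immediately after baseline evaluations". The same sentence adds that a confidence level will accompany the prediction. Section 2.3.3 expects "instantaneous recommendations by artificial intelligence on which stimulation frequency is best suitable for a subject", and describes the output as a ranking that can guide clinical evaluation.

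Out-of-sample checking is described under Aim 2.1: "We will use techniques such as cross-validation (e.g., leave-one-out) and bootstrapping to examine the generalizability of the models". The intervals there are for predicted values. Aim 2.2 takes over the Aim 2.1 techniques only where possible.

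No section says how two sets of predicted gait values become a best frequency, how large a difference must be, what is reported when the two predictions are nearly equal, or what result would count as support for the Section 9.1 hypothesis.

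**The concern.** The Section 9.1 hypothesis concerns a difference within a patient: does baseline information tell us which frequency suits this patient better? The planned models are fitted to gait levels. Patients differ widely in gait level, and baseline gait should predict later gait well whichever frequency is on. A model can therefore do well on its fitted targets and carry no information about the choice between frequencies.

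Three safeguards are absent: a minimum difference or no-preference outcome, a stated use for the confidence level, and a comparison with one frequency for everybody. The last matters most. If one frequency were better for all patients by the same amount, a model recommending it to everyone would look right every time, although baseline data had predicted nothing about individuals.

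Section 2.1 says the study will prepare a randomized trial of selecting patients for 60 Hz before surgery. A claim of predictability that rests on gait-level accuracy would be a weak basis for that trial.

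**Working it through.** **The plan's own figure.** Section 9.2 is the only design calculation: 15.79 × 0.03 / 0.14² = 24.2, reported as 24, with 30 to be recruited. It reproduces, but it rests on a healthy-versus-Parkinson's gait speed contrast and does not address Aim 2.2. The documents give no figure for Aim 2.2, so what follows is conditional.

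**Step 1. Gait accuracy and choice of frequency are separate.** Write patient i's gait as mᵢ + δᵢ/2 on 60 Hz and mᵢ − δᵢ/2 on HFS. Suppose δᵢ = 0 for everyone. Assumptions:
- Variance of mᵢ is 0.03 (m/s)², borrowed from the healthy pooled variance in Section 9.2.
- The error SD e of one prediction is 0.03, 0.05 or 0.10 m/s. The documents give none.
- Errors are normal and independent between the two frequencies. If they were positively correlated, the gaps below would be smaller.

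Accuracy for the patient's true gait level is R² = 1 − e²/0.03. If the better prediction is chosen, the average predicted gap in favour of the chosen frequency is SE × √(2/π) = 0.80 SE, with SE = e√2.

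| e (m/s) | R² for gait level | Average predicted gap (m/s) | Mean gain on independent held-out gait |
|---|---|---|---|
| 0.03 | 1 − 0.0009/0.03 = 0.97 | 0.034 | 0 |
| 0.05 | 1 − 0.0025/0.03 = 0.92 | 0.056 | 0 |
| 0.10 | 1 − 0.0100/0.03 = 0.67 | 0.113 | 0 |

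In simulation the held-out gain was zero to three decimals, and the recommendation agreed with the observed better frequency 50% of the time. R² would be lower against observed gait, which carries measurement error, but the separation is the same.

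**Step 2. Effect of a no-preference zone.** Take the same no-difference case and name a frequency only when the interval for the predicted 60 Hz minus HFS difference excludes zero. If coverage is nominal, the share of patients labelled is 1 minus the confidence level: 20% at 80%, 10% at 90%, 5% at 95%. At 95% that is 24 × 0.05 = 1.2 of 24 patients, or 30 × 0.05 = 1.5 of 30. The chance of at least one false label, with independent patients, is 1 − 0.95²⁴ = 0.71 or 1 − 0.95³⁰ = 0.79. The zone limits false labels but does not test the hypothesis.

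**Step 3. Why the comparator is one frequency for all.** Let rᵢ be the recommendation for patient i from a model fitted without that patient, and s₋ᵢ the frequency with the better mean in the remaining patients. With gait Y scored so that higher is better,

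G = mean over i of [Yᵢ(rᵢ) − Yᵢ(s₋ᵢ)].

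If frequency makes no difference, G has expectation zero. If one frequency is better for everyone and the model recommends it throughout, every term is zero. G is positive only when the model departs from the common choice in patients who actually do better for it.

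**The case against.** The strongest reply is that the plan states no forced-choice rule. The conversion from predictions to a best frequency is left open, a confidence level is promised, and the output is called a ranking to guide clinicians. A patient with no preference could be shown with low confidence. Cross-validation is also mentioned.

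Much of this stands, and it rules out stronger readings a reader might infer:
- That the plan always names one frequency, and so labels 100% of patients, half to each frequency, under no effect. No section says so. Full labelling follows only if the better prediction is simply taken.
- That it will report a false benefit. No section says the gain of the selected setting will be reported, and under no effect that gain is zero on independent held-out data.
- That the models learn from coin-flip labels. Aim 2.2 models continuous gait values. The two-group classification in Section 4.2 is earlier work.
- That the study cannot detect whether frequency matters. Aim 1.1 tests the average difference with a mixed model and Holm-Bonferroni adjustment. The gap concerns differences between patients in which frequency is better.

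The reply does not close the gap. The confidence level has no stated level, target quantity or consequence, and intervals for single predicted values are not intervals for their difference. Cross-validation applies to Aim 2.2 only where possible, and checking gait predictions out of sample leaves the choice of frequency unchecked.

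**Conclusion.** The point holds as an underspecification of a primary aim that should be corrected. Aim 2.2 has a two-way target and no minimum difference, no no-preference outcome, no stated role for the confidence level and no comparison with a single frequency for all. Followed as written, it could support a claim of predictability when frequency makes no difference.

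The size cannot be read from the documents, which give no error for a predicted difference. The illustration shows that R² of 0.67 to 0.97 for gait speed is compatible with zero gain from the recommendation, given the assumed variances and independent errors. These figures are not properties of the plan.

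**What to change.** Add to Section 9.4.2, Aim 2.2:

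1. Produce leave-one-patient-out predictions from baseline data, holding out all of a patient's trials together. Score the recommended frequency on that patient's observed gait. Report the gain G against the best single frequency for all, chosen in the training patients, with a bootstrap interval over patients. Claim that the best frequency is predictable only if that interval lies above zero. The gait measure, its direction and the handling of the four contact pairs must be named beforehand.
2. Compute the planned bootstrap interval for the predicted 60 Hz minus HFS difference, state its level, and report no preference when it includes zero. This is an analysis label, not a programming instruction.

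The two Stand and Walk (SAW) tests per trial may look like a ready error estimate, but they share the trial's own error. With between-trial variance assumed at 0.5 or 1 times walk variance, a nominal 5% threshold built on them fires in 14% or 22% of patients under no effect. Choosing the best of 8 settings on the first walk and scoring it on the second keeps a false gain of 0.58 or 1.01 walk SDs. They should not be used for this purpose.

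The cost is SAP wording and analysis of data already planned. Fewer patients will receive a definite recommendation, and the reported performance may be less favourable. Leave-one-out training sets overlap, so the interval for G is approximate.

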9.4.3 ANALYSIS OF THE SECONDARY ENDPOINT(S)

Secondary endpoints will be factored into the regression modeling for AIM 2.

9.4.4 SAFETY ANALYSES

Not applicable

9.4.5 BASELINE DESCRIPTIVE STATISTICS

Refer to section 9.4.1

9.4.6 PLANNED INTERIM ANALYSES

Not applicable

9.4.7 SUB-GROUP ANALYSES

The subgroup analyses will be analyzed based on age, gender, and disease duration for both primary and secondary endpoints.

9.4.8 TABULATION OF INDIVIDUAL PARTICIPANT DATA

Individual participant data will be listed by measure and time point.

9.4.9 EXPLORATORY ANALYSES

Not applicable

10 SUPPORTING DOCUMENTATION AND OPERATIONAL CONSIDERATIONS

10.1 REGULATORY, ETHICAL, AND STUDY OVERSIGHT CONSIDERATIONS

10.1.1 INFORMED CONSENT PROCESS

10.1.1.1 CONSENT/ASSENT AND OTHER INFORMATIONAL DOCUMENTS PROVIDED TO PARTICIPANTS

A consent form describing in detail the study intervention, study procedures, and risks is given to the participant and written documentation of informed consent is required prior to starting intervention/administering study intervention.

10.1.1.2 CONSENT PROCEDURES AND DOCUMENTATION

Informed consent is a process that is initiated prior to the individual's agreeing to participate in the study and continues throughout the individual's study participation. Consent forms will be Institutional Review Board (IRB)-approved and the participant will be asked to read and review the document. The investigator will explain the research study to the participant and answer any questions that may arise. A verbal explanation will be provided in terms suited to the participant's comprehension of the purposes, procedures, and potential risks of the study and of their rights as research participants. Participants will have the opportunity to carefully review the written consent form and ask questions prior to signing. The participants should have the opportunity to discuss the study with their family or surrogates or think about it prior to agreeing to participate. The participant will sign the informed consent document prior to any procedures being done specifically for the study. Participants must be informed that participation is voluntary and that they may withdraw from the study at any time, without prejudice. A copy of the informed consent document will be given to the participants for their records. The informed consent process will be conducted and documented in the source document (including the date), and the form signed, before the participant undergoes any study-specific procedures. The rights and welfare of the participants will be protected by emphasizing to them that the quality of their medical care will not be adversely affected if they decline to participate in this study.

In the event that consent is obtained during Study Visit 1, we request a waiver of written documentation of consent for the dopaminergic medication withdrawal to take place 12 hrs prior to this visit. This waiver will not affect data validity, subject safety, or one's willingness to participate.

10.1.2 STUDY DISCONTINUATION AND CLOSURE

This study may be temporarily suspended or prematurely terminated if there is sufficient reasonable cause. Written notification, documenting the reason for study suspension or termination, will be provided by the suspending or terminating party to study participants, investigator, funding agency, and regulatory authorities. If the study is prematurely terminated or suspended, the Principal Investigator (PI) will promptly inform study participants, the Institutional Review Board (IRB), and sponsor and will provide the reason(s) for the termination or suspension. Study participants will be contacted, as applicable, and be informed of changes to study visit schedule.

Circumstances that may warrant termination or suspension include, but are not limited to:

- Determination of unexpected, significant, or unacceptable risk to participants
- Demonstration of efficacy that would warrant stopping
- Insufficient compliance to protocol requirements
- Data that are not sufficiently complete and/or evaluable
- Determination that the primary endpoint has been met
- Determination of futility

Study may resume once concerns about safety, protocol compliance, and data quality are addressed, and satisfy the sponsor and/or IRB.

10.1.3 CONFIDENTIALITY AND PRIVACY

Participant confidentiality and privacy is strictly held in trust by the participating investigators and their staff. This confidentiality is extended the clinical information relating to participants. Therefore, the study protocol, documentation, data, and all other information generated will be held in strict

confidence. No information concerning the study or the data will be released to any unauthorized third party without prior written approval of the sponsor.

All research activities will be conducted in a private and controlled setting.

The collected data will include self-reported demographic information as well as clinical and sensor based measurements. A REDCap (Research Electronic Data Capture) database will be created for the purposes of this project at Northwell Health. This is a secure web based research data management application in which demographic data, baseline DBS parameters, and daily levodopa equivalent dose will be stored. Data will be de-identified and stored securely in a HIPAA compliant manner. A unique study identification number will identify individual participants and their research data. The clinical research coordinator will input data into this database within 24 hours of acquiring clinical data for each subject.

All sensor based data will be stored on secured research laptop and backed up to an encrypted external hard-drive regularly. Paper copies of all research materials as well as backup copies of sensor data and the database will be stored on encrypted portal storage devices that will be kept securely in the PI's office. All research and data storage equipment will be stored in the PI's office in a locked cabinet.

Each subject will have a unique identification number that will be used for all assessments. The PI and Research coordinator will conduct routine monitoring and cleaning of the data to ensure accuracy. The dataset will be de-identified and shared with the research team at the University of Tennessee Knoxville in adherence to the resource-sharing plan.

To further protect the privacy of study participants, a Certificate of Confidentiality will be issued by the National Institutes of Health (NIH). This certificate protects identifiable research information from forced disclosure. It allows the investigator and others who have access to research records to refuse to disclose identifying information on research participation in any civil, criminal, administrative, legislative, or other proceeding, whether at the federal, state, or local level. By protecting researchers and institutions from being compelled to disclose information that would identify research participants, Certificates of Confidentiality help achieve the research objectives and promote participation in studies by helping assure confidentiality and privacy to participants.

